6.2.1 Serious Adverse Event Collecting and Reporting

Following the subject's written consent to participate in the study, all SAEs, whether related or not related to study drug, will be collected, including those thought to be associated with protocol-specified procedures. All SAEs will be collected that occur within 30 days of discontinuation of dosing or within 30 days of the last visit for screen failures. If applicable, SAEs will be collected that relate to any later protocol-specified procedure (e.g., a follow-up skin biopsy).

The investigator will report any SAE occurring after these time periods that is believed to be related to study drug or protocol-specified procedure at 90 days and 180 days period

An SAE report will be completed for any event where doubt exists regarding its status of seriousness.

If the investigator believes that an SAE is not related to study drug, but is potentially related to the conditions of the study (such as withdrawal of previous therapy, or a complication of a study procedure), the relationship will be specified in the narrative section of the SAE Report Form.

All SAEs, whether related or unrelated to saxagliptin, and all pregnancies will be reported to BMS (by the investigator or designee) within 24 hours.

All SAEs should be reported via confirmed facsimile (fax) transmission, or scanned and reported via electronic mail to:

SAE Email Address: [contact]

SAE [contact]

SAEs will be reported on MedWatch Form 3500A, which can be accessed at: <http://www.accessdata.fda.gov/scripts/medwatch/>.

MedWatch SAE forms should be sent to the FDA at:

MEDWATCH
[name]
[name]
Fax: [name] ([name])
<http://www.accessdata.fda.gov/scripts/medwatch/>

All SAEs should simultaneously be faxed or e-mailed to BMS at:

Global Pharmacovigilance & Epidemiology
Bristol-Myers Squibb Company
[contact]
Email: [contact]

If an ongoing SAE changes in its intensity or relationship to study drug or if new information becomes available, a follow-up SAE report should be sent within 24 hours to the BMS using the same procedure used for transmitting the initial SAE report. All SAEs should be followed to resolution or stabilization.

6.2.2 Non-Serious Adverse Events (NSAEs) Collecting and Reporting

The collection of non-serious adverse event (NSAE) information will begin at initiation of study drug. NSAE information will be collected from the start of a placebo lead-in period or other observational period intended to establish a baseline status for the subjects. NSAEs will be followed to resolution or stabilization, or reported as SAEs if they become serious. Follow-up as required for NSAEs that cause interruption or discontinuation of study drug, or those that are present at the end of study treatment as appropriate will be undertaken. All identified NSAEs will be documented appropriately.

6.3 Laboratory Test Abnormalities

All laboratory test results captured as part of the study will be recorded following institutional procedures. Test results that constitute SAEs should be documented and reported as such.

The following laboratory abnormalities should be documented and reported appropriately:

- any laboratory test result that is clinically significant or meets the definition of an SAE
- any laboratory abnormality that required the subject to have study drug discontinued or interrupted
- any laboratory abnormality that required the subject to receive specific corrective therapy.

6.4 Overdose

An overdose is defined as the accidental or intentional administration of any dose of a product that is considered both excessive and medically important. All occurrences of overdose will be reported as an SAE.

6.5 Pregnancy

If, following initiation of the investigational product, it is subsequently discovered that a study subject is pregnant or may have been pregnant at the time of investigational product exposure, including during at least 6 half lives after product administration, the investigational product will be permanently discontinued in an appropriate manner (e.g., dose tapering if necessary for subject safety). Protocol-required procedures for study discontinuation and follow-up must be performed on the subject unless contraindicated by pregnancy (e.g., x-ray studies). Other appropriate pregnancy follow-up procedures should be considered if indicated.

The investigator or designee will immediately notify the BMS (or designee) Medical Monitor of this event and complete and forward a Pregnancy Surveillance Form to BMS (or designee) within 24 hours and in accordance with SAE reporting procedures described in Section 7.2.1.

Follow-up information regarding the course of the pregnancy, including perinatal and neonatal outcome and, where applicable, offspring information will be reported on the Pregnancy Surveillance Form.

Any pregnancy that occurs in a female partner of a male study participant should be reported to the sponsor. Information on this pregnancy will be collected on the Pregnancy Surveillance Form.

6.6 Potential Drug-Induced Liver Injury (DILI)

Wherever possible, timely confirmation of initial liver-related laboratory abnormalities should occur prior to the reporting of a potential DILI event. All occurrences of potential DILIs, meeting the defined criteria, must be reported as SAEs (see Section 7.2.1 for reporting details).

Potential drug induced liver injury is defined as

1. AT (ALT or AST) elevation > 3 times upper limit of normal (ULN)

AND
2. Total bilirubin > 2 times ULN, without initial findings of cholestasis (elevated serum alkaline phosphatase),

AND
3. No other immediately apparent possible causes of AT elevation and hyperbilirubinemia, including, but not limited to, viral hepatitis, pre-existing chronic or acute liver disease, or the administration of other drug(s) known to be hepatotoxic.

6.7 Other Safety Considerations

Any significant worsening noted during interim or final physical examinations, electrocardiograms, x-rays, and any other potential safety assessments, whether or not these procedures are required by the protocol, should also be recorded as a nonserious or serious AE, as appropriate, and reported accordingly.

7 DATA MONITORING COMMITTEE

Not Applicable.

8 STATISTICAL CONSIDERATIONS

Statistical Analysis:

Sample Size Estimation:

The total sample size requested, accounting for attrition over the 12-week period, is 21 subjects per group or 42 subjects total.

Sample size estimates were based on the effects of exercise on CD34+/KDR+ cells and VEGF, as described in the literature⁴⁷⁻⁵⁰. The effect of a single session, as well as extended training, on healthy subjects or those with existing cardiovascular conditions appears to increase the CD34+/KDR+ cells and VEGF.

To compute sample size we used the approach suggested by Diggle, Liang, & Zeger (1994)⁵¹ which compares the rates of change in the two study groups over time. This approach incorporates the number and interval of time points and the correlation among repeated measures. For this study, we will employ one baseline and two follow-up measures at 6 and 12 weeks. Further, we will assume a correlation 0.60 among repeated measures of the outcome. [We consider this a conservative estimate since Frison and Pocock (1992)⁵² suggest a correlation of 0.65 as reasonable in the absence of an existing estimate. We also note that as this correlation increases, statistical power also increases.

The results in the table below show the expected mean difference in study groups at the end of follow-up, as well as the average rate of change in the two groups at 80% power and 90% power. To estimate the effect of saxagliptin on the CD34+/KDR+ cells, we expect that the effect would be at least 25% greater than the effect seen for exercise alone. Using the results from Sandri et al. (2005)⁴⁹ for the rate of change and the variability, the CD34+/KDR+ cells increased an average rate of about 4/wk with a standard deviation of about 15. Thus, for a 25% increase in the rate of change for the CD34+/KDR+ cells due to saxagliptin, a sample size of 18 subjects per group would provide about 84% power, assuming measures taken at baseline and 2 equally-spaced time points over 12 weeks. At the conclusion of follow-up, we would expect study groups to differ by an average of 12 cells. If the effect of saxagliptin is only 20%, a sample of 18 would provide about 70% power, whereas a sample of 20 would provide about 73% power.

For VEGF, the results from Sandri et al. (2005)⁴⁹ were mixed with one study group showing a .6 pg/mL per week increase and another showing a 0.5 pg/mL per week decrease after 4 weeks of training. If we assume that saxagliptin will increase VEGF consistently at 0.3 pg/mL per week difference in slopes compared with exercise alone, then assuming a standard deviation of 5 and correlation of 0.60 among repeated measures, a sample size of 18 per group would provide about 77% power to detect a difference in slopes of 0.3 pg/mL per week or a mean difference in the groups at the end

of the study of 3.6 pg/mL. A sample size of 27 would provide about 90% power to detect the same effects.

Thus, we feel that a sample size of at least 18 subjects per group with complete data would provide sufficient power for the study outcomes. In order to insure that we will have 18 per group who complete the study, we will enroll 20 subjects per group in order to account for attrition over the 12-week period.

Biochemical Measure	Mean difference at end of 12 weeks	Sample Size per group	Power
CD34+/KDR+ cells	12 cells (25% increase; 4/wk vs. 5/wk)	18	0.84
		22	0.90
VEGF, pg/mL	3.6 pg/mL (50% increase; (0.6/wk vs. 0.9/wk)	18	0.77
		27	0.90

Data Analysis.

The distributional assumptions of all measures will be examined. Means and standard deviations will be computed for continuous measures and proportions for categorical variables. Graphical representations of the mean group slopes and individual slopes will be generated and inspected. Study groups will be compared to determine whether any imbalance between the groups on patient characteristics remain after randomization. If imbalance is evident, by inspection, all models will be adjusted for the unbalanced covariates. Change in outcome over time will be examined using a multilevel approach with linear mixed models (LMM)^{53,54}. The longitudinal multilevel modeling approach will enable us to examine characteristics of within-person change, as well as between-group differences that may influence change. LMMs handle missing data more efficiently than traditional ANOVA designs. In the linear mixed models, the patient is considered a random effect and the outcome measured at specific time points is nested within patient. In an initial model containing only the variable TIME, we will use a likelihood ratio test to determine whether a random effect for time should be modeled. The model below represents a random intercept for patient and a random coefficient for TIME.

$$Y_{ij} = \beta_0 + \beta_1 Time_{ij} + u_{i0} + u_{i1} Time_{ij} + \varepsilon_{ij}$$

We will examine whether TIME may be modeled linearly by testing the added contribution of TIME (represented with two indicator variables) to a model with TIME as a single continuous variable. Assuming time may be modeled as a continuous variable, subsequent analyses will add study group and other patient characteristics as covariates. We are particularly interested in whether there is a significant interaction between study group and time, adjusting for other patient level covariates. A significant interaction would indicate that the slopes in outcome over time differ by study group. If the global test of interaction is significant, subsequent significance testing of the pair wise comparisons of group slopes group will be adjusted for multiple comparisons. The model also includes coefficients for the group-by-time interactions and random effects for patient and time.

$$Y_{ij} = \beta_0 + \beta_1 Time_{ij} + \beta_2 Group_i + \beta_3 (Time_{ij} \times Group_i) + u_{i0} + u_{i1} Time_{ij} + \varepsilon_{ij}$$

In the event that TIME is modeled using indicator variables, two indicator variables will be used to represent the three time points, with baseline serving as the reference category. The interaction between GROUP and TIME will be modeled in a similar fashion using two additional indicator variables. The above multivariable model enables us to adjust for time-varying covariates, such as glucose. Since glucose will be measured contemporaneously with the outcomes at each visit, however, causal interpretations of glucose and any outcome are suspect. As such, we will consider glucose as a nuisance covariate, and consider any relationship between glucose and an outcome as merely associative.

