Exclusion Criteria:	
Patients with:
 
 1. Contraindications for moderate exercise 2. Implanted devices (e.g., pacemakers) that may interact with Tanita scale 3. Previous coronary or cerebrovascular event within 6 months of screening or active or clinically significant coronary and/or peripheral vascular disease 4. Low hematocrit (< 28 UNITS). 5. Pre-existing liver disease and/or ALT and AST $>2.5 \times$ UNL 6. Kidney disease at levels defined by: serum creatinine levels ≥ 1.5 mg/dL for men, ≥ 1.4 mg/dL for women, estimated CrCl ≤ 50 mL/min 7. History of pancreatitis, or cancer (except basal cell carcinoma) 8. Statin use started (or dose change) in the last 3 months, 9. Use of oral or injectable anti-diabetic medication other than Metformin 10. Daily use of a consistent long-term steroid medication (oral, inhaled, injected) within the last 3 months 11. Systolic BP > 140 mmHg and Diastolic BP > 90 mmHg at screening visit. 12. Active wounds or recent surgery within 3 months. 13. Inflammatory disease, or chronic current use of anti-inflammatory drugs within the last 3 months. 14. triglycerides >400 mg/dL 15. untreated hyper/hypothyroidism 
Additionally, patients who are active smokers, patients who are pregnant, nursing women, and post-menopausal women who are on hormone replacement therapy will be excluded.
 
Patients on low dose oral contraceptives will be allowed to participate as these formulations contain lesser amount of estrogens.

----------------------------	---

Criteria for Evaluation: (Efficacy, safety, stopping rules, etc.)	Subjects will be screened at week -4, then evaluated for end points at weeks 0, 6 and 12. Study participation will be stopped for adverse effects at the discretion of the study investigator. Subjects may stop study participation at any time and for any reason.
Statistics:	The total sample size requested, accounting for attrition over the 12-week period, is 20 subjects per group or 40 subjects total. Sample size estimates were based on the effects of exercise on CD34+/KDR+ cells as described in the literature. The effect of a single session, as well as extended training, on healthy subjects or those with existing cardiovascular conditions appears to increase the CD34+/KDR+ cells. This will provide 73% power (see statistics section). A p-value of less than 0.05 will be considered statistically significant.

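### The stated powers match a one-sided 5% test, but the planned group-by-time test is two-sided at 0.05, so the headline 84% power is about 76.5%

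*Combined protocol and SAP*

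**What the plan says.** Section 8, Sample Size Estimation, compares the two groups' rates of change from a baseline and two follow-up measures (weeks 6 and 12), with a correlation of 0.60 between repeated measures. Its power claims are:

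- CD34+/KDR+ cells, 25% faster rise (5 against 4 per week, SD 15): "a sample size of 18 subjects per group would provide about 84% power". The table adds 0.90 at 22 per group.
- CD34+/KDR+ cells, 20% faster rise: "a sample of 18 would provide about 70% power, whereas a sample of 20 would provide about 73% power".
- VEGF, SD 5: "a sample size of 18 per group would provide about 77% power to detect a difference in slopes of 0.3 pg/mL per week". The text and table add 90% at 27 per group.

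Neither the significance level nor the sidedness appears in the power calculation. The only criterion is in the synopsis, under Statistics: "A p-value of less than 0.05 will be considered statistically significant". The test itself is in Section 8, Data Analysis, where the group-by-time interaction is examined in a linear mixed model: "A significant interaction would indicate that the slopes in outcome over time differ by study group".

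On size, the Statistics row of the synopsis says the total, allowing for attrition, "is 20 subjects per group or 40 subjects total", and ties this to 73% power. Section 8 opens by saying that the total, also allowing for attrition, "is 21 subjects per group or 42 subjects total". It later plans to enrol 20 per group so that 18 complete.

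**The concern.** A power figure has to refer to the test that will be run. Testing whether two slopes differ, in either direction, at p < 0.05 is a two-sided test with critical value 1.960. If the powers were computed with the one-sided value 1.645, each is too high for the planned analysis.

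This matters because Section 8 rests the trial's size on these figures: it concludes that 18 completers per group give enough power for the study outcomes. If the figures are too high, that conclusion fails for the one scenario shown above 80% at 18 per group. A null result would then be read against a power that the trial does not have.

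**Working it through.** **Inputs (all from Section 8).** Visits at 0, 6 and 12 weeks; correlation ρ = 0.60; SD 15 (CD34+/KDR+) or 5 (VEGF). Slope differences d:

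- 25% effect: 0.25 × 4 = 1.0 cell per week (12 cells at week 12)
- 20% effect: 0.20 × 4 = 0.8 cell per week
- VEGF: 0.3 pg/mL per week (3.6 pg/mL at week 12)

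**Formula.** For equally correlated repeated measures, the variance of a patient's slope is SD²(1 − ρ)/S, where S is the sum of squared deviations of the visit times. The mean time is 6 weeks, so S = 36 + 0 + 36 = 72. For n completers per group:

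z = d / √[2 · SD² · (1 − ρ) / (72 n)], and power = Φ(z − c), with c = 1.645 (one-sided 5%) or 1.960 (two-sided 5%).

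**Headline case.** With d = 1, SD = 15, n = 18: 2 × 225 × 0.40 / (72 × 18) = 180/1296, so z = √7.2 = 2.683.

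- One-sided: Φ(2.683 − 1.645) = 85.0%, close to the stated 84%.
- Two-sided: Φ(2.683 − 1.960) = 76.5%.

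**All six figures.**

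| Scenario | n per group | z | Stated | One-sided 5% | Two-sided 5% | Two-sided, t critical value |
|---|---|---|---|---|---|---|
| CD34+/KDR+, 25% | 18 | 2.683 | 84% | 85.0% | 76.5% | 74.1% |
| CD34+/KDR+, 25% | 22 | 2.966 | 90% | 90.7% | 84.3% | 82.6% |
| CD34+/KDR+, 20% | 18 | 2.147 | 70% | 69.2% | 57.4% | 55.0% |
| CD34+/KDR+, 20% | 20 | 2.263 | 73% | 73.2% | 61.9% | 59.7% |
| VEGF | 18 | 2.415 | 77% | 77.9% | 67.5% | 65.0% |
| VEGF | 27 | 2.958 | 90% | 90.5% | 84.1% | 82.7% |

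The one-sided column agrees with the plan throughout. The two-sided normal column falls short by about 6 to 13 percentage points.

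**Solving for n at 90% power.** n = 2 · SD² · (1 − ρ) · (c + 1.282)² / (72 d²).

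- CD34+/KDR+, 25%: the multiplier is 180/72 = 2.5. One-sided, 2.5 × 2.927² = 21.4, so 22. Two-sided, 2.5 × 3.242² = 26.3, so 27.
- VEGF: the multiplier is 20/(72 × 0.09) = 3.086. One-sided, 26.4, so 27. Two-sided, 32.4, so 33.

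The table's sample sizes for 90% power, 22 and 27, are exactly the one-sided solutions.

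**Synopsis.** The 73% there equals Section 8's figure for 20 patients per group and a 20% effect. In the synopsis, 20 is the number enrolled after allowing for attrition. Section 8 expects 18 of those 20 to complete, for which its own figure is 70%. The synopsis does not name the effect size.

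**Enrolment.** 20 per group: synopsis Study Schema and Statistics, Study Design Overview, and the end of the sample-size text in Section 8. 21 per group or 42 in total: synopsis accrual goal, Section 4.1, and the start of Section 8.

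**The case against.** **Sidedness is inferred.** The protocol never says two-sided, and its aims are directional: it expects saxagliptin to improve endothelial function. This is correct, and it limits the claim. But the analysis text describes an overall, non-directional interaction test, and no one-sided test is declared. If one-sided 5% was intended, the plan would still need correcting, because a reader cannot tell that the powers depend on it.

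**Other two-sided calculations come close.** With the same inputs, a two-sided analysis of covariance at week 12 gives 85.1, 91.3, 67.0, 71.6, 77.0 and 91.1%. A mixed model constrained to a common baseline gives 85.7, 91.7, 67.8, 72.3, 77.8 and 91.6%. Each is within 2 points of five stated figures, and each misses the 70%. So the one-sided match cannot prove how the figures were produced. Neither alternative is the documented method, however: Section 8 compares rates of change, and its model has an unconstrained group term. Nor does a different correlation help. Matching the six figures two-sided would take values from about 0.665 to 0.70, against the stated 0.60.

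**Eighteen completers is pessimistic.** The mixed model also uses partial data from dropouts. With full retention, two-sided power for the 25% effect is 80.7% at 20 per group or 82.6% at 21. That softens the shortfall, but both remain below 84%, and the plan itself sizes the trial on 18.

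**Part of this is already disclosed.** The plan itself shows VEGF at 77% and the 20% effect at 70% for 18 per group. Only the 25% scenario newly drops below 80%, but that is the scenario on which the sample size chiefly rests.

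**The synopsis and enrolment conflicts are separate and minor.** Agreed. They are included because the same edit resolves them.

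**Conclusion.** The concern holds. Under the planned interaction test, read as two-sided at 0.05, the powers at 18 completers per group are 76.5% (CD34+/KDR+, 25% effect), 57.4% (20% effect) and 67.5% (VEGF), where the plan states 84%, 70% and 77%. No scenario reaches 80% at the size the plan relies on. For the 25% effect, 80% two-sided power needs 20 completers per group.

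These figures rest on the plan's own SDs, correlation and effects, equal correlation across visits, linear time and a normal approximation. A t critical value lowers them by about 2 points. The formula has no between-patient variation in slopes, although the planned model allows a random time effect; adding such variation would lower power further. The two-sided reading is inferred from the analysis text. The synopsis's 73% and the conflict between 20 and 21 per group are plain inconsistencies and need no such inference.

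**What to change.** 1. In Section 8, state that the group-by-time interaction is tested two-sided at 0.05, and give that level in the power calculation.
2. Restate the powers in the text and table. CD34+/KDR+, 25% effect: 76.5% (18 per group) and 84.3% (22). 20% effect: 57.4% (18) and 61.9% (20). VEGF: 67.5% (18) and 84.1% (27). If 90% rows are kept, they need 27 and 33 per group. Reword the conclusion that 18 per group is sufficient to match.
3. In the synopsis, replace the 73% with the two-sided power at 18 completers and name the effect: 76.5% for 25%, or 57.4% for 20%.
4. Use one enrolment figure, 20 or 21 per group, in the synopsis, Section 4.1, the Study Design Overview and Section 8.

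If a one-sided 5% test really was intended, the plan must say so and justify it; the Section 8 powers could then stand, but items 3 and 4 would still be needed, with 70% for a 20% effect or 84% for 25% in the synopsis.

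The cost is an edit to text and table, with no added patients, visits or procedures. The price is a less favourable stated power.

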1.1.5 Clinical Efficacy of Saxagliptin

Saxagliptin Phase 2b and Phase 3 worldwide clinical development program in T2DM included eight studies in which over 4600 subjects combined with the results from clinical pharmacology studies support the oral dose of saxagliptin 5 mg once daily as the usual clinical dose in a wide range of subjects with T2DM, as either monotherapy, add-on combination therapy with metformin, a thiazolidinedione (TZD), or a sulfonylurea (SU), or initial combination therapy with metformin.

In the Phase 2b dose-ranging study, administration of saxagliptin 5 mg was associated with significant inhibition of plasma DPP-4 activity at the trough of the dosing interval as well

as clinically meaningful decreases in A1C, fasting plasma glucose (FPG), and postprandial serum glucose. The results from the short-term periods of the Phase 3 studies confirmed clinically meaningful benefits of saxagliptin 5 mg on A1C, as well as FPG, postprandial glucose, insulin, C-peptide, and glucagon levels. In the monotherapy studies (CV181011 and CV181038), add-on combination therapy studies (CV181014, CV181013, CV181040 with metformin, TZD, glyburide, respectively), and initial combination study with metformin (CV181039), treatment with saxagliptin produced statistically significant reductions in A1C relative to control. A greater percentage of subjects treated with saxagliptin achieved target glycemic goals including A1C levels < 7% compared with subjects treated with placebo or active comparator. The saxagliptin 5 mg groups achieved greater reductions from baseline in A1C than the saxagliptin 2.5 mg groups in five of the six core Phase 3 studies (one of the core studies, Study CV181039, did not have a 2.5 mg treatment group). There was no consistent evidence for an incremental efficacy benefit for 10 mg beyond that seen for the 5 mg dose.

Saxagliptin treatment consistently demonstrated a beneficial antihyperglycemic effect across subgroups of demographic and baseline diabetes characteristics.

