²⁰where Sitagliptin was compared to placebo with endothelial progenitor cells as a outcome measure in patients with type 2 diabetes over 4 weeks. Though our study is over 12 weeks we do not anticipate significant drop in HbA1C in between the two groups in this relatively short time period to act as a confounding factor on CD34+ cell number, function and gene expression. Most clinical studies looking at HbA1C reduction were of a much longer duration of 6 months or above and most DPP-4 inhibitor studies are with animal EPCs where comparison with human CD34+ population is difficult to make. In one study⁵⁸ where saxagliptin was used for 12 weeks in drug-naïve type 2 diabetes patients there was placebo-subtracted HbA1c reduction noted of 0.45-0.63%. It showed mean placebo-subtracted reductions in fasting serum glucose of 20 mg/dL. From our laboratory studies of in vitro human EPC studies we do not think glucose level change of 20 mg/dL is significant enough to account for changes in EPC number, function and gene expression. However we will take this possibility into account during statistical analysis of the results between the saxagliptin and placebo groups.

Lifestyle Intervention for Type 2 diabetes patients²:

To keep uniformity within the cohort regarding lifestyle during the length of the study duration, all patients at entry will ideally receive dietary advice from the research coordinator, a diabetes educator, a registered dietitian (as per American Diabetes Association clinical guidelines²), specifically geared towards type 2 diabetes patients. They will be advised to adhere to 150 minutes of weekly aerobic exercise (50-70% of maximal heart rate) as best as possible. Patient's activity will be monitored using accelerometers and will be downloaded at regular intervals by the research coordinator.

Subjects will be taking 5.0 mg of Onglyza (saxagliptin) or placebo. We choose to use the maximum approved dose of saxagliptin in order to discern a definite effect.

Visits with outcome measurements will be scheduled for morning following overnight 10 hours fast to reduce diurnal variability, and clinical parameters will be obtained at scheduled office visits as depicted in the study schema and will be measured at each outcome visit as follows:

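### The plan does not say whether the powered group-by-time test is read with or without post-randomization glucose, and it states an equal sex split in both arms that no described allocation rule delivers.

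*Combined protocol and SAP*

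**What the plan says.** **Glucose.** Section 6.2 cites a 12-week saxagliptin study in drug-naive patients: "It showed mean placebo-subtracted reductions in fasting serum glucose of 20 mg/dL". It judges a change of that size too small to explain changes in the cells, then adds: "However we will take this possibility into account during statistical analysis of the results between the saxagliptin and placebo groups". Section 8 writes a mixed model whose only by-time term is time by group, with no glucose term. It states the aim as: "We are particularly interested in whether there is a significant interaction between study group and time, adjusting for other patient level covariates". After the equations it adds "The above multivariable model enables us to adjust for time-varying covariates, such as glucose", notes that causal readings of glucose and outcome are suspect, and concludes "we will consider glucose as a nuisance covariate, and consider any relationship between glucose and an outcome as merely associative".

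**Sex.** Section 4.1 states flatly that each arm will hold men and women in equal numbers. The Week -4 paragraph of Section 6.2 makes equal recruitment an aim. Section 5.3 specifies permuted blocks and gives neither a stratification factor nor a block size.

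**Baseline covariates.** Section 8 compares the groups after randomization and says: "If imbalance is evident, by inspection, all models will be adjusted for the unbalanced covariates". It gives no covariate list, no threshold and no timing relative to another step in the same paragraph: "Graphical representations of the mean group slopes and individual slopes will be generated and inspected".

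**The concern.** Glucose at weeks 6 and 12 is measured after randomization, and the drug under test is a glucose-lowering drug. Section 1.1.5 reports that earlier Phase 3 studies "confirmed clinically meaningful benefits of saxagliptin 5 mg on A1C, as well as FPG". If part of any effect on the cells runs through glucose, the model without glucose estimates the total effect and the model with glucose estimates what remains. Section 8 powers the first. The hypothesis in Sections 1.3 and 4.1, an effect over and above glycemic control, points toward the second. With both available and neither named as primary, the reader cannot tell which one the trial will be judged on.

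On sex, the protocol claims a design property that its allocation method, as described, does not produce. If change over 12 weeks differs between men and women, a chance imbalance shifts the estimate in that trial.

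**Working it through.** **1. The plan's own figure.** Inputs from Section 8: SD 15, correlation 0.60, weeks 0, 6 and 12, slope difference 1 cell/week (4 vs 5), 18 per group.
- Sum of squared deviations of time: 36 + 0 + 36 = 72.
- Per-patient slope SD: 15 × √(0.40/72) = 1.118.
- SE of the slope difference: 1.118 × √(2/18) = 0.373 per week, so 12 × 0.373 = 4.47 cells at week 12.
- Planned effect over SE: 12/4.47 = 2.68.
- Power by the normal formula: 85.0% one-sided at 0.05 (the plan says 84%) and 76.5% two-sided. With a t reference, two-sided power is 75.4%.

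The plan does not state sidedness. The glucose figures below start from 75.4% for that reason. The gap to 84% is a separate matter.

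**2. Size of the glucose shift.** Adjusted difference = 12 − γ × d, where d is the placebo-subtracted fall in glucose and γ is the number of cells lost per mg/dL of higher glucose. The documents give d = 20, in drug-naive patients, so 10 is also shown. They give no γ; the values below are assumptions.

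| γ (cells per mg/dL) | d = 10 | d = 20 |
|---|---|---|
| 0 | 12 | 12 |
| 0.05 | 11.5 | 11 |
| 0.1 | 11 | 10 |
| 0.2 | 10 | 8 |

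**3. Power.** Assumed glucose SDs: 25 mg/dL between patients, 10 to 30 within.
- *γ = 0, as Section 6.2 expects.* The SE becomes √(4.47² + d² × Var(γ̂)). Two-sided power is 71.3% to 73.9% at d = 20 and 74.1% to 74.6% at d = 10. The cost is about 1 to 4 points.
- *γ = 0.2.* If residual variance is held at the plan's value, power at d = 20 is about 40% (within-patient SD 15) or 41% (SD 30). But if SD 15 is the total outcome SD, adjustment also removes the variance that glucose explains. At within-patient SD 30, residual within-patient variance falls from 225 × 0.40 = 90 to 90 − 0.2² × 30² = 54, and the basic SE falls to 12 × √(54 × 2/(18 × 72)) = 3.46. The ratio of effect to SE is then about 8/3.46 = 2.31 at d = 20 and 10/3.46 = 2.89 at d = 10, against 2.68 unadjusted. Power becomes about 61% at d = 20 (44% at SD 15) and *rises* to 81% at d = 10.

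The shift in the estimate is therefore clear given γ and d. The change in power is not.

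**4. Sex split.** Assume exactly 20 men and 20 women, 20 per arm, no strata, and enrollment order unrelated to sex. The number of men in one arm is then hypergeometric (40, 20, 20).
- P(10/10 in both arms) = C(20,10)²/C(40,20) = 0.248.
- P(12 vs 8 or worse) = 0.343.
- P(13 vs 7 or worse) = 0.113.
- At the 21 per group given at the start of Section 8, an equal split within an arm is impossible. With 21 men and 21 women, the nearest split (11/10) occurs with probability 2 × 0.2311 = 0.462.

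A 12 vs 8 split shifts the week-12 difference by (12 − 8)/20 = 0.2 times any sex difference in 12-week change: 0.6 cells if that difference is an assumed 3 cells, 1.2 if it is 6.

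**5. Covariates chosen by inspection.** In one simulated complete dataset, the group-by-time estimate was 0.3049 (SE 0.3614) both with and without sex and age as main effects. Simulations used 20 per arm with 2 per arm losing visits, and six assumed covariates. Taking the most favorable subset of flagged covariates raised null rejection by 0.1 to 0.4 points. The week-12 difference moved by a median of 0.06 cells (95th percentile 0.27), or 0.18 (0.68) when each covariate correlated 0.3 with outcome level.

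**The case against.** **Glucose.** The plan does not overlook it. Section 6.2 anticipates no significant HbA1c difference between the groups and no material effect of a 20 mg/dL change on the cells. Calling glucose a nuisance covariate can be read as a commitment to include it, and Section 8 warns against causal readings. This stands, but the warning concerns the relation between glucose and the outcome. It does not address what adjustment does to the group-by-time coefficient, and the written model still omits glucose. A reader might infer that adjustment would cost the trial much of its power. The documents do not support that: the coefficient is unknown, and power can rise once residual variance falls.

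**The sponsor's choice.** An effect over and above glycemic control is central to the hypothesis, so making glucose adjustment secondary is not the only defensible answer. That is right. The requirement is that one version be named as primary in advance.

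**Sex.** Section 6.2 already speaks of an aim, and Section 5.3 does not rule out strata. Both are true, but Section 4.1 still makes the flat statement and no section describes how it would be met. A reader might infer a biased comparison. Randomization remains valid; the issue is chance imbalance and an unsupported statement.

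**Covariates.** A reader might infer that choosing covariates by eye inflates false positives. Under the written model, with time by group as its only by-time term, it does so negligibly. Covariate-by-time terms could move the estimate (0.313 against 0.3049 in the same dataset), but the equation does not contain them.

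**Conclusion.** Two parts hold.

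(A) The role of glucose in the powered group-by-time test is open. This is a cheap improvement, not an error in the model. Its size is γ × d: 0.5 to 4 of the planned 12 cells over the assumed ranges, and zero if glucose does not affect the cells. In that last case, including it costs about 1 to 4 points of power. No firm statement about power is possible otherwise.

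(B) The equal sex split in Section 4.1 is wrong as written, because the described allocation does not deliver it. It would be met 25% of the time under the favorable assumption of exactly 20 and 20, and never at 21 per arm. How much an imbalance moves the result depends on a sex difference in change that the documents do not give.

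The by-inspection covariate rule is a minor note and does not carry the point. The textual findings are secure. The cell shifts rest on the stated assumptions.

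**What to change.** **Section 8, after the glucose sentences, add:** *Glucose is not in the primary group-by-time model. A model adding time-varying glucose is reported as a labeled secondary analysis of the hypothesis that the effect goes beyond glycemic control.* The cost is two sentences. The downside is that the hypothesis in Sections 1.3 and 4.1 is then tested as a secondary analysis. If the sponsor wants it primary, the plan must say so before unblinding and restate the power for the adjusted effect.

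**Section 5.3:** stratify the permuted blocks by sex for subjects not yet randomized. This needs a second randomization list and can leave up to two incomplete blocks. If allocation is finished, correct Section 4.1 to an overall recruitment aim, matching Section 6.2. A main effect for sex is not a substitute, since it does not remove a sex difference in slope.

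**Optional tidying:** replace the inspection rule with a short covariate list fixed before unblinding. This has no material effect on the result.

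None of these changes needs extra patients or visits.
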